PRogram In Support of Moms: An Innovative Stepped-Care Approach for Obstetrics and Gynecology Clinics (PRISM)

NCT02760004

Document Date:5/9/23

Analysis plan

Our general approach to statistical analysis followed commonly accepted procedures. All analyses were conducted using SAS 9.4. As a first step in analysis, descriptive statistics and measures of association including measures of central tendency and measures of dispersion were used to summarize all variables. This analysis included graphical analysis of distributional characteristics of all variables. Bivariate associations between explanatory variables of interest were assessed by student t-tests, Wilcoxon rank-sum, and Chi-square tests for continuous, ordinal, and categorical values, respectively.

Data analysis Hypothesis 1. *Depressed perinatal patients receiving care from clinics enrolled in PRISM will experience more improvement in depression symptoms than patients receiving care from the enhanced usual care clinics (2 point difference-of-difference in EPDS)* To answer the specific hypothesis included in this difference-in-differences analysis aim we used unadjusted repeated measures linear regression models with the EPDS score as the dependent variable and the group (PRISM/MCPAP for Moms) and two time periods as the independent variables along with the interaction term of group by time period. The estimates of the difference in time points between groups was reported along with 95% confidence intervals (CI), p-values and the sample size (n).

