Data analysis Hypothesis 2. *Depressed perinatal patients receiving care from clinics enrolled in PRISM will have improved treatment initiation and sustainment (as measured by attendance and one initial mental health assessment or treatment visit and an average ≥ 1 mental health visit every 1 months until remission of symptoms or study assessment) as compared to women receiving care from clinics enrolled in enhanced usual care.* Our primary outcome in this hypothesis was treatment initiation and sustainment, which was operationalized as receipt of prescription by an obstetrician, attendance in mental health visit(s), and adherence to medication, all of which were represented as dichotomous variables. Specifically, we used logistic regression to calculate odds ratios, corresponding confidence intervals and p-values to determine the impact of treatment group (PRISM/MCPAP) on treatment initiation and sustainment. These models were run both unadjusted and accounting for clustering of practices within treatment groups using Mixed Model analysis with clinic as a random effect.

Sub-hypothesis. *Depressed women receiving care from the enhanced usual care clinics will experience a small amount of improvement in depression and treatment participation at 12 months postpartum as compared to during pregnancy or immediately postpartum.* We anticipated that the enhanced usual care clinic will also experience improvement in both depression and treatment participation. As such we repeated the analyses outlined in H1 and H2 specifically within each of the treatment arms. In this instance, however, instead of considering a treatment by time interaction we only evaluated the time effect.

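### The Hypothesis 2 logistic models leave out EPDS at entry, so a realised difference between arms in severity would pass into the odds ratio; the likely effect is modest

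*SAP*

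**What the plan says.** Data analysis Hypothesis 2 takes treatment initiation and sustainment as the outcome and breaks it into three dichotomies: "receipt of prescription by an obstetrician, attendance in mental health visit(s), and adherence to medication". For the model, the SAP states "we used logistic regression to calculate odds ratios, corresponding confidence intervals and p-values to determine the impact of treatment group (PRISM/MCPAP"). On adjustment it says "These models were run both unadjusted and accounting for clustering of practices within treatment groups", the second version "using Mixed Model analysis with clinic as a random effect". Treatment group is the only explanatory term named. The Additional analyses section lists subgroup, moderation and mediation work but no adjustment of Hypothesis 2 for symptom severity.

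Hypothesis 1 is handled differently. It uses "unadjusted repeated measures linear regression models with the EPDS score as the dependent variable", with group and "two time periods as the independent variables along with the interaction term of group by time period". An EPDS value from an earlier time period therefore exists, and the starting level is differenced out. The SAP does not say outright that the first period is study entry. The inference is reasonable, because the Sub-hypothesis compares 12 months postpartum with an assessment in pregnancy or soon after delivery.

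**The concern.** How ill a woman is at entry plausibly affects whether she is prescribed medication, attends visits or adheres. The hypothesis itself links treatment to symptoms by counting visits "until remission of symptoms or study assessment". Care is compared between whole clinics, so case mix can differ between arms by more than it would if individual women were allocated. Hypothesis 1 protects itself against such a difference; Hypothesis 2 has nothing equivalent, although the variable needed appears to be in the data already. At stake is how far the Hypothesis 2 odds ratios reflect the programme and how far they reflect which arm had the more severely depressed women at the start.

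**Working it through.** The SAP gives no sample size, number of clinics, participation rate, EPDS standard deviation (SD), intraclass correlation (ICC) or target odds ratio for Hypothesis 2. There is no plan figure to reproduce, and **every input below is an assumption**.

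**1. Does the clinic random effect remove an arm difference?** Write logit(p) = a + θ·arm + β·EPDS + u, where u is a clinic intercept with mean zero. Leave EPDS out, and let the arms differ by Δ in mean entry EPDS. The arm coefficient then estimates roughly θ + βΔ, shrunk a little by averaging over the spread of EPDS. Differences among clinics within an arm go largely into u. The difference between arms cannot, because all women in a clinic share an arm and u has mean zero in both arms.

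**2. Size of the shift when there is no treatment effect (true odds ratio 1).**

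| Assumed inputs | Strength per EPDS point | Odds ratio, Δ = 1 | Odds ratio, Δ = 2 |
|---|---|---|---|
| SD 4, participation about 40% | odds up 5%, 10%, 15% | 1.05, 1.10, 1.14 | 1.10, 1.20, 1.30 |
| SD 4.5, control rate 30% | log odds ratio 0.05, 0.10, 0.15 | 1.05, 1.10, 1.15 | 1.10, 1.21, 1.31 |

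As a hand check on the second row, exp(0.10 × 1) = 1.105 before averaging, against 1.100 after. If EPDS does not predict the outcome, the odds ratio stays at 1.00.

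**3. How often chance alone gives a 1-point arm difference, if clinics were randomised.** With K clinics per arm and m women per clinic:

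SD of the arm difference = sqrt(2·SD²·(1 + (m − 1)·ICC) / (m·K))

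With SD 4, m = 30 and ICC 0.05, the numerator is 2 × 16 × (1 + 29 × 0.05) = 78.4.

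- K = 3: sqrt(78.4/90) = 0.933; chance of more than 1 point either way 28%
- K = 5: sqrt(78.4/150) = 0.723; 17%
- K = 8: sqrt(78.4/240) = 0.572; 8%

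With SD 3, each value is multiplied by 0.75, and the chances fall to 15%, 6.5% and 2%. With SD 4.5, 5 to 10 clinics per arm, 15 or 30 women per clinic and ICC 0 to 0.10, the SD of the arm difference runs from 0.37 to 1.14 points.

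**4. Attenuation, standard error and power.** With the second-row inputs and perfect balance, a conditional odds ratio of 2 becomes 1.98, 1.94 or 1.88 when EPDS is left out. The next figures come from 400 simulated trials per setting: 5 clinics per arm, 30 women each, true log odds ratio 0.693, log odds ratio per EPDS point 0 to 0.15, ICC 0 to 0.10, residual clinic SD 0 or 0.3 on the logit scale.

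| | Without EPDS | With EPDS |
|---|---|---|
| Mean log odds ratio | 0.63 to 0.70 | 0.69 to 0.71 |
| Model standard error | 0.241 to 0.243 | 0.244 to 0.255 |
| Estimate / empirical SD, 0.10 per point | 2.09 to 2.77 | 2.14 to 2.87 |
| Same, 0.15 per point, ICC 0.10, clinic SD 0.3 | 1.98 | 2.18 |
| Same, 0.15 per point, ICC 0.10, clinic SD 0 | 2.42 | 2.77 |

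At 0 to 0.05 per point there is essentially no gain. At 0.15 per point with ICC 0.10, the spread of estimates across trials was slightly larger without EPDS (0.267 against 0.257 with clinic SD 0; 0.318 against 0.315 with clinic SD 0.3). That is the chance imbalance of step 3, and the model standard error does not show it.

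A separate set of 1,500 simulated trials per setting (150 women per arm, log odds ratio 0.65, odds up 5%, 10% or 15% per point) gave power without and then with EPDS of 78.5% and 79.0%, 78.6% and 79.6%, and 73.8% and 75.9%. The simulation error of one power figure is about sqrt(0.785 × 0.215/1500) = 1.1 percentage points.

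The 400-trial simulations fitted ordinary logistic models, so the statement about the random effect rests on step 1, not on simulation.

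**The case against.** An unadjusted comparison beside a clinic random-effect model is a legitimate and clearly stated choice. If clinics were randomised, an imbalance in entry EPDS is chance: it adds variance rather than expected bias, and the random-effect interval is meant to carry between-clinic variance. The shift is also small. With a standard error of about 0.23, ln(1.05)/0.23 = 0.2 and ln(1.14)/0.23 = 0.6, so a 1-point difference moves the estimate by 0.2 to 0.6 of a standard error, and half of such imbalances would count against PRISM. The participants are all depressed, so a narrower EPDS spread is plausible. The remission wording concerns symptom course after entry, and it sits in the hypothesis, not in the three dichotomies. All of this stands, and it limits the point to a modest one. It does not remove it: adjustment corrects the imbalance that actually occurred, at almost no cost.

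A reader might infer several stronger things that the document does not support:

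- **Any difference between clinics biases the result.** Only a difference between arms shifts the odds ratio.
- **Precision is lost because the standard error grows.** In logistic regression, leaving out a predictor attenuates the odds ratio; the model standard error was slightly smaller without EPDS.
- **The Hypothesis 2 result is confounded.** That needs non-random allocation or recruitment that differs by arm, and the SAP establishes neither.
- **Only a model containing severity protects against severity-related dropout.** Weighting or imputation that uses severity would also do so, and the SAP does not say that dropout depends on severity.
- **Hypothesis 2 already handles starting level through time.** The Sub-hypothesis speaks of replacing a treatment-by-time interaction for both hypotheses, but the Hypothesis 2 section names no time term.

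**Conclusion.** The point holds as a modest, inexpensive improvement. Both Hypothesis 2 models omit a severity measure that appears to be in hand, and a realised arm difference in that measure would enter the odds ratio despite the clinic random effect. For a 1-point difference and no treatment effect, the odds ratio would be about 1.05 to 1.15. The gain in power from adjusting is about 0.5 to 2 percentage points (79.0 − 78.5 = 0.5; 75.9 − 73.8 = 2.1), too small to be the main argument.

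The conclusion rests on two inferences: that severity at entry predicts the three outcomes, and that the first EPDS period is study entry. The sizes rest wholly on assumed inputs. Whether an imbalance would be chance or confounding depends on how clinics were allocated, which this document does not state.

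**What to change.** For each of the three Hypothesis 2 outcomes, add EPDS at entry as a continuous covariate to the logistic model with the clinic random effect, and report the result beside the same model without EPDS. State in the SAP that the first EPDS time period is study entry, if it is.

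Hypotheses 1 and 2 are written up in the past tense in a document dated 5/9/23. If those analyses are already done, the adjusted model must be labelled as added afterwards and must not be presented as prespecified. The text should also say that the adjusted odds ratio is conditional on EPDS and is not the same quantity as the unadjusted one, so some gap between the two is expected even with balanced arms.

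The cost is a sentence or two in the SAP and a rerun on data already held.

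### The within-arm test of change in treatment participation repeats H2, whose stated models have no time term and do not link a woman's records; if participation was recorded in both periods, its standard errors ignore the pairing

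*SAP*

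**What the plan says.** The SAP's Sub-hypothesis expects a small "improvement in depression and treatment participation at 12 months postpartum as compared to during pregnancy or immediately postpartum". One instruction covers both outcomes: "we repeated the analyses outlined in H1 and H2 specifically within each of the treatment arms", with the change that "instead of considering a treatment by time interaction we only evaluated the time effect".

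The two analyses to be repeated are built differently.

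- Data analysis Hypothesis 1 (EPDS): "we used unadjusted repeated measures linear regression models with the EPDS score as the dependent variable". The terms are group and "two time periods as the independent variables along with the interaction term of group by time period".
- Data analysis Hypothesis 2 (initiation and sustainment, as dichotomous variables): "we used logistic regression to calculate odds ratios, corresponding confidence intervals and p-values". The stated purpose of these models is "to determine the impact of treatment group (PRISM/MCPAP) on treatment initiation and sustainment". They are fitted once unadjusted, and again "accounting for clustering of practices within treatment groups using Mixed Model analysis with clinic as a random effect".

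**The concern.** The instruction to swap an interaction for a time effect works for H1. Take out group and the interaction, and a repeated measures model with time remains. It does not work for H2, where the only stated explanatory term is treatment group. Within one arm that term is constant and drops out, so nothing is left to test.

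The Sub-hypothesis names time as the tested effect, so a time term is implied. Adding it to either stated H2 form still leaves no term that ties together two records from the same woman. A clinic intercept captures what women at one clinic share, not what one woman's two records share. If the same women contribute a binary record in each period and those records are correlated, the precision reported for the change in participation is wrong.

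**Working it through.** **1. The stated models side by side**

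| Feature | H1 (EPDS) | H2 (participation) |
|---|---|---|
| Time term | yes | none stated |
| Group-by-time interaction | yes | none stated |
| Link between a woman's records | repeated measures | none stated |
| Clinic term | none stated | random effect in one of two runs |

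No other section of the SAP supplies a longitudinal model for a binary outcome. The SAP gives no sample size, rate, correlation or number of clinics for this analysis, so there is no figure of its own to reproduce. Every input below is an assumption.

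**2. Within-woman correlation alone**

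Take n women, each seen twice, with participation p1 and p2 and within-woman correlation rho.

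- Variance of the log odds ratio if records are treated as independent: 1/(n·p1·q1) + 1/(n·p2·q2).
- True variance: the same, minus 2·rho/(n·√(p1·q1·p2·q2)).
- With p1 = p2, reported SE / true SE = 1/√(1 − rho).

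| rho | SE ratio | True size of a nominal 5% test |
|---|---|---|
| 0.2 | 1/√0.8 = 1.118 | 2.8% |
| 0.4 | 1/√0.6 = 1.291 | 1.1% |
| 0.6 | 1/√0.4 = 1.581 | 0.2% |

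Simulation of ordinary logistic regression (100 women, 30% in both periods, 20,000 data sets per value) gave sizes of 2.6%, 1.2% and 0.2%. McNemar's paired test stayed near 5%.

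The price is power. For n = 100 and a change from 30% to 40%, the independent-records SE is √(1/21 + 1/24) = 0.299. At rho = 0.4 the true SE is √(0.0893 − 0.0356) = 0.232. Power is 0.27 when the pairing is ignored and 0.48 when it is used.

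**3. Does the clinic random effect repair this?**

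Both H2 forms with time added were simulated (one arm, 10 clinics of 20 women, 30% in both periods, clinic SD 0.3 on the logit scale, no clinic-by-period variation, 1,000 runs per cell). At correlations of about 0.2, 0.37 and 0.55 the SE ratio was 1.11, 1.28 and 1.48 unadjusted, and 1.11, 1.27 and 1.47 with the clinic random effect. It does not.

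**4. Clinic-by-period variation acts the other way**

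Let d be the correlation between two women of one clinic in the same period, minus that in different periods. With m women per clinic, SE ratio = 1/√(1 − rho + (m − 1)·d). For m = 20:

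| d | rho 0.2 | rho 0.4 | rho 0.6 |
|---|---|---|---|
| 0 | 1.118 | 1.291 | 1.581 |
| 0.01 | 1.005 | 1.125 | 1.302 |
| 0.02 | 0.921 | 1.010 | 1.132 |

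The two errors cancel at d = rho/19, that is 0.011, 0.021 and 0.032. Above that, the reported SE is too small.

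**5. Does step 4 apply only to participation?**

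No. A model that handles the pairing but has no clinic-by-period term has SE ratio √((1 − rho)/(1 − rho + 19d)). This is √(0.80/0.99) = 0.90 at rho 0.2 and d 0.01, and √(0.40/0.78) = 0.72 at rho 0.6 and d 0.02. The H1 model, with no clinic term stated, is of this kind.

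**The case against.** The strongest objection is that the two records may not exist. H2 describes a first visit and then an average visit frequency kept up to remission or the study assessment. That reads like one cumulative outcome per woman. If so, there is no pairing to ignore, and the standard-error argument does not apply. This stands as a condition on the point, but it does not rescue the text: a change over time cannot be tested without an early value.

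A second objection is that the SAP never writes down a logistic model with time and no woman-level term, and that H1's repeated-measures structure could be meant to carry over. That is possible, but repeated measures is stated only for the EPDS model, and the instruction is to repeat H2. An analyst who follows the H2 text and adds time gets the model examined above.

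A third is that the sizes are wholly assumed and fall on both sides of no error, with ratios from 0.92 to 1.58 in step 4. This stands in full. The calculation shows how the error arises and not how large it was in this trial.

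Finally, the contrast is an uncontrolled before-after comparison within an arm and carries no between-arm conclusion. That also stands, and it sets the severity.

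**Conclusion.** The point holds, conditionally, and is minor. The within-arm participation analysis is defined by reference to a model that has no interaction to replace, no time term and no link between a woman's records. If participation was recorded in both periods for the same women and the records are correlated, the standard errors, confidence intervals and p-values of its time effect are wrong. With within-woman correlation alone, assumed at 0.2 to 0.6, the reported SE is about 1.12 to 1.58 times the true one.

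Three stronger readings might be inferred and are not supported.

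- *The intervals are too wide, so the test is merely conservative.* Clinic-by-period variation can cancel or reverse this, and the SAP gives nothing from which to judge it. The net direction is not established.
- *The standard errors are known to be wrong.* The SAP does not show that participation has two records per woman.
- *Only participation is touched, or, conversely, the between-arm results fall too.* The missing woman-level link concerns the participation time effect alone and does not affect the H2 between-arm comparison, which has no time term. The clinic-by-period source is not specific to participation and would apply to H1 as well.

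**What to change.** For each participation outcome recorded in both periods, replace the repeated H2 model in the Sub-hypothesis with one stated within-arm model: mixed logistic regression with a fixed effect of time and random intercepts for clinic and for woman within clinic. This keeps the clinic effect that H2 already uses and adds the missing link.

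Label the odds ratio as woman-specific and report the proportion in each period beside it, because the two scales differ. For 30% to 40%, the population-average odds ratio is (0.4/0.6)/(0.3/0.7) = 1.56, while the woman-specific one is 1.74, 2.11 and 3.21 at rho 0.2, 0.4 and 0.6 (normal woman intercept).

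If the H2 outcome is a single follow-up measure with no early-period value, remove participation from the Sub-hypothesis.

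The cost is one extra model on existing data and about two sentences in the SAP. The model restores the pairing only. Clinic-by-period variation remains outside it and is better considered once, for H1 and participation together.

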Additional analyses. A number of additional analyses are planned that will examine changes in patient level measures, as well as heterogeneity of the treatment effect, and will enable us to better understand how the intervention works and whether it works better for certain subset populations. We will examine the impact of gestational age or length postpartum on EPDS score. Additionally, we will test for both moderation and mediation. Specifically, we expect to conduct subgroup analysis by race/ethnicity, SES, psychiatric comorbidity, and practice type. To identify potential mediators we will use the classic method of mediation analysis as outlined by Baron and Kenny.¹²⁶ Mediation analysis seeks to understand the mechanisms through which the intervention has its effect. Therefore, measure of treatment fidelity and implementation are potential key mediators. To formally test for mediation we will use a technique developed by Karlson, Holm, and Breen,¹²⁷⁻¹²⁹ which decomposes the association of an independent variable with a given outcome into a direct and indirect (mediated) component in the context of a generalized linear model. This type of analysis will directly inform the dissemination plan by clueing us into which components of this multi-faceted intervention are responsible for substantial portions of observed effectiveness.

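### The SAP puts a causal-steps screen ahead of its mediation test; applied in classic form, it makes a significant total arm effect a precondition that an indirect effect does not need

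*SAP*

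**What the plan says.** The SAP's Additional analyses paragraph gives two mediation methods two jobs, in this order:

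- Causal steps: "To identify potential mediators we will use the classic method of mediation analysis".
- Decomposition: "To formally test for mediation we will use a technique", described as one that "decomposes the association of an independent variable with a given outcome into a direct and indirect (mediated) component".

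Between the two it explains what mediation is for and names candidates on conceptual grounds: "measure of treatment fidelity and implementation are potential key mediators". It adds: "This type of analysis will directly inform the dissemination plan".

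The paragraph does not list the causal steps, set a significance level for them, require a significant total effect of arm, or say that a candidate failing the first method is kept from the second. It is written in the future tense, whereas the H1 and H2 sections report analyses already done.

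**The concern.** In its classic form the causal-steps method asks for three significant results: the total effect of arm on outcome, the effect of arm on the mediator, and the effect of the mediator on outcome given arm. Naming the method without modification brings the first condition in. An indirect effect does not need it: the total effect can be too small to detect, or can be cancelled by a direct effect of opposite sign, while the mediator is working.

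The screen also yields no estimate or interval for the indirect effect. The decomposition supplies that anyway, so the first step can remove candidates but adds no information about those that remain. What is at stake is the advice on which components of the intervention carry its effect, which the SAP intends to feed into dissemination.

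**Working it through.** The SAP gives no sample size, SD, alpha or power, and no figure for the mediation analysis, so there is nothing of its own to reproduce. The only relevant number in it is the 2-point EPDS difference-of-differences in Hypothesis 1. Everything else below is assumed.

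**Inputs (assumed).** Two-sided 5% tests; 1:1 arms; n patients in total; independent patients; linear models with unit residual SDs; arm-to-mediator path a = 0.5; mediator-to-outcome path b = 0.3; direct effect c′ varied. The total effect is c′ + ab, and ab = 0.5 × 0.3 = 0.15. Effects are in residual SD units.

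**Step 1: the ceiling set by the total-effect test.** Ignoring the mediator, the outcome's within-arm SD is √(1 + b²) = √1.09 = 1.044, so SE = 2 × 1.044/√n. For n = 200 this is 0.148. With c′ = 0, z = 0.15/0.148 = 1.02 and power is about 17%. The same formula gives 24% at n = 300 and 30% at n = 400.

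**Step 2: the two mediator paths.** At n = 200, z for a is 0.5/(2/√200) = 3.54 (power 94%) and z for b is 0.3 × √200 = 4.24 (power 99%). The product is 0.94 × 0.99 = 0.93.

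**Step 3: simulation, 2,000 trials per setting.** The screen requires all three tests to be significant and the direct effect to be reduced. The comparator requires a and b only.

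| Direct effect c′ | Total effect | Screen, n = 200 / 300 / 400 | a and b only |
|---|---|---|---|
| 0 | 0.15 | 16 / 24 / 30% | 93 / 99 / 100% |
| 0.15 | 0.30 | 51 / 69 / 81% | same |
| 0.25 | 0.40 | 73 / 91 / 97% | same |
| 0.40 | 0.55 | 90 / 98 / 100% | same |
| −0.15 | 0 | 2 to 3% | same |

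The standard error of a simulated 16% is √(0.16 × 0.84/2,000) = 0.8 percentage points, so the first row agrees with the ceiling in Step 1.

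**Step 4: where the H1 target falls.** Two points is 2/5 = 0.4 SD at an assumed SD of 5, with a range of 2/6 = 0.33 to 2/4 = 0.5. The 0.40 row is therefore the one nearest the planned effect, and the 0.15 row describes a disappointing H1 result.

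**Step 5: a second set-up on the EPDS scale.** Outcome SD 5, a = 0.5, b = −2 (indirect effect −1), 4,000 runs. The comparator is a product-of-coefficients test, standing in for the decomposition's indirect component in a linear model. Detection at 50 / 100 / 150 per arm:

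| Direct effect | Total effect | Screen, then indirect test | Indirect test alone |
|---|---|---|---|
| 0 | −1 | 14 / 28 / 40% | 58 / 93 / 99% |
| −1 | −2 | 37 / 77 / 92% | 58 / 93 / 99% |
| +1 | 0 | 3 / 4 / 6% | 57 / 93 / 99% |

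Power for a 2-point total effect, which is the ceiling in the second row, is 52%, 81% and 93% at those sizes.

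Both set-ups agree. The loss is severe when the total effect is small, near-total when direct and indirect effects oppose, and modest when the total effect is well powered.

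**The case against.** The strongest reply is that the SAP contains no gate. A reader might infer a stated rule that real mediators are discarded whenever the total arm effect is not significant. The text does not support that: it has no drop rule, alpha or total-effect condition, and it already names fidelity and implementation measures as candidates, so every candidate might go on to the decomposition. This stands, and it is why the point is conditional. It does not remove the point, because on that reading the first step does no work and the link between the two methods is still not fixed.

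Three other inferences should also be resisted.

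- **That the total effect is always the weakest of the three tests.** This depends on the path sizes. With a = 0.3, b = 0.15 and a total effect of 0.4 at n = 200, power is 79% for the total effect, 56% for a and about 55% for b. The screen then costs little: 24% against 30%.
- **That the decomposition alone would be well powered.** The comparators assume independent patients and patient-level mediators. The SAP describes arms made up of clinics and does not say at what level fidelity and implementation are measured. If they are clinic-level, the same paths with an assumed 20 clinics, 300 patients and ICC 0.02 give about 18% without any screen. The a path then has z of only 0.5/(2/√20) = 1.12.
- **That a null H1 would leave the SAP's mechanism question unanswered because of the screen.** The stated aim is to apportion observed effectiveness, and with a null H1 there is little to apportion. An indirect effect could still exist and be worth reporting, but that goes beyond the declared purpose.

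**Conclusion.** The point holds in conditional form, at minor severity. The SAP assigns causal steps to identification and the decomposition to testing. If the classic steps are used as a screen, detection is capped by the power of the total-effect test, for a condition that mediation does not require. Around the H1 target (0.4 SD at an assumed SD of 5) the cost is 20 percentage points at n = 200 (93 − 73) and 3 at n = 400 (100 − 97). At a total effect of 0.15 SD it is about 70 points or more (93 − 16 = 77 at n = 200; 100 − 30 = 70 at n = 400).

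These sizes rest on assumed paths, sample sizes and SD, and on independent patients. Clinic clustering or clinic-level mediators would lower power with or without the screen. The analysis is one of several described by "A number of additional analyses are planned", so the conclusions on H1 and H2 do not depend on it.

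**What to change.** Delete the sentence that assigns identification to the causal-steps method. In its place:

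- list the candidate mediators, starting from the fidelity and implementation measures already named, and state whether each is measured on the patient or the clinic;
- state that every listed candidate goes to the planned decomposition whatever the significance of the total arm effect;
- report each indirect effect with a confidence interval that accounts for clinic.

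The edit needs no new data and removes one step. The cost is a few more decompositions to report, the work of producing clinic-based intervals, and the prospect that those intervals are wide if clinics are few.

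### The mediation analysis is planned in a generalized linear model with no stated clinic effect although arm is set by clinic, so the direct-effect test, and in some settings the mediated-effect test, can be too liberal

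*SAP*

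**What the plan says.** - **Method (SAP, Additional analyses).** Mediators are first identified: "To identify potential mediators we will use the classic method of mediation analysis". The formal test then decomposes the association "into a direct and indirect (mediated) component in the context of a generalized linear model". Neither step mentions a clinic random effect, a cluster-robust variance or a multilevel model.
- **Candidate mediators (same section).** "measure of treatment fidelity and implementation are potential key mediators".
- **Use of the result (same section).** "This type of analysis will directly inform the dissemination plan".
- **Unit that sets the arm (SAP, Data analysis Hypothesis 1).** The hypothesis concerns "Depressed perinatal patients receiving care from clinics enrolled in PRISM", compared with patients of the enhanced usual care clinics. Arm is therefore a property of the clinic.
- **Where clinic is handled (SAP, Data analysis Hypothesis 2).** The logistic models are run without adjustment and also "accounting for clustering of practices within treatment groups using Mixed Model analysis with clinic as a random effect". This carries by reference to the sub-hypothesis: "As such we repeated the analyses outlined in H1 and H2 specifically within each of the treatment arms". The Hypothesis 1 model is described as unadjusted. No other clinic term is stated.

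**The concern.** Every woman in a clinic has the same arm. The arm-to-mediator path and the direct effect of arm therefore rest on differences between clinics. If the mediator takes one value per clinic, the mediator-to-outcome path does too. A single-level generalized linear model treats women as independent, so it credits these paths with more information than the clinics supply. Standard errors and p-values are then too small.

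What is at stake is the conclusion about mechanism. The section expects the analysis to show which components account for the benefit and to steer dissemination. Chance differences between clinics could be reported as a direct effect, or as mediation through a particular component.

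**Working it through.** **Inputs.** From the SAP: arm set by clinic, a generalized linear model, no clinic term. The SAP states no number of clinics, clinic size, ICC or effect size for this analysis, so there is no planned figure to reproduce. Assumed: 5 or 10 clinics per arm, 10 or 30 women per clinic (m), ICC from 0 to 0.05, nominal two-sided level 0.05.

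**Step 1: formula for a naive arm contrast.** Design effect DE = 1 + (m − 1) × ICC; actual error = 2 × [1 − Φ(1.96/√DE)].

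| m | ICC | DE | Actual error |
|---|---|---|---|
| 10 | 0.02 | 1 + 9 × 0.02 = 1.18 | 0.071 |
| 10 | 0.05 | 1 + 9 × 0.05 = 1.45 | 0.104 |
| 30 | 0.02 | 1 + 29 × 0.02 = 1.58 | 0.119 |
| 30 | 0.05 | 1 + 29 × 0.05 = 2.45 | 0.21 |

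**Step 2: simulated direct effect, true value 0, no clinic term.** Linear models with balanced clinics give 0.11 to 0.13 (ICC 0.02) and 0.21 to 0.22 (ICC 0.05) with 30 women per clinic, and 0.07 to 0.08 and 0.09 to 0.12 with 10. These agree with the formula. The rate is somewhat lower when arm shifts a patient-level mediator strongly. With 10 clinics of 30 women, a 1 SD shift and mediator ICC equal to outcome ICC, it is 0.09 at ICC 0.02 and 0.18 at ICC 0.05. At ICC 0 the test is at its nominal level.

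**Step 3: simulated mediated effect, true value 0, 30 women per clinic, no clinic term.** The test is the product of coefficients with a delta-method standard error and |z| > 1.96. The screen means that a significant total effect is also required. The SAP does not spell out the steps of its stepwise method, so both readings are shown. The true direct effect is 0 in this table.

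| Setting | No screen | With screen |
|---|---|---|
| Clinic-level mediator, unchanged by arm, 0.3 SD effect on outcome, outcome ICC 0 | about 0.7 | 0.24 to 0.28 |
| Same, 0.1 SD effect | 0.17 to 0.39 | 0.02 to 0.04 |
| Clinic-level mediator, changed 2 SD by arm, no effect on outcome, outcome ICC 0.02 | 0.12 to 0.13 | 0.01 to 0.02 |
| Same, outcome ICC 0.05 | 0.20 to 0.21 | 0.04 to 0.05 |
| Patient-level mediator, unchanged by arm, 0.3 SD effect, mediator ICC 0.05, outcome ICC 0.02 | 0.18 to 0.19 | 0.03 to 0.04 |

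If the true direct effect is 0.5 SD, the screen is mostly passed. The first row with the screen then becomes 0.58 to 0.72.

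Some settings show no inflation even without the screen. For a patient-level mediator with mediator ICC 0, a 0.3 SD effect and outcome ICC 0.02, the rate is 0.03 to 0.04. With 10 women per clinic, the patient-level settings unchanged by arm are all at 0.00 to 0.06.

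**Step 4: does accounting for clinic restore the level?** The arm-to-mediator path was fitted on clinic records. The outcome path used a random intercept, or the equivalent clinic-mean regression for a clinic-level mediator. Requiring both paths to be significant on t references gives a false-positive rate of 0.00 to 0.055 for the mediated effect. The direct-effect test, with t on clinics − 3 degrees of freedom, gives 0.016 to 0.059. A product test with a normal reference reaches 0.067, against at most 0.044 with t on clinics − 3, which is why the small-sample correction matters. Cluster-robust and bootstrap versions were not simulated.

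**The case against.** The strongest reply is that the section is silent, not wrong. The phrase about a generalized linear model describes what the cited technique does, and such a model can be run with cluster-robust errors. That is fair: a reader might infer that the SAP rules out clinic adjustment, and it does not. But this SAP states clustering where it is used, in Hypothesis 2, and there distinguishes an unadjusted run from one that accounts for clinic. Silence in the mediation section is therefore not safely read as implied adjustment, and an analyst who followed it literally would leave clinic out.

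Three further objections limit the point, and they stand.

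- **Mediator level.** A reader might count it as a defect that the SAP does not say whether fidelity and implementation are measured per clinic or per patient. The protocol, which is not shown, commonly defines this, so it is not a finding. It matters here only because the size of the error depends on it.
- **The 0.7 figure.** A reader might take it as the expected error. It needs a clinic-level mediator that arm does not change but that affects outcome. For fidelity to and implementation of this intervention, no arm difference is the less plausible case. It also needs no screen on the total effect, or a sizeable true direct effect.
- **Linear models.** The planned decomposition itself was not simulated, and the Hypothesis 2 outcomes are dichotomous. The rates illustrate the mechanism and do not predict this trial's error.

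The screening argument does not touch the direct-effect rates.

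**Conclusion.** The point holds in a limited form. Followed as written, the mediation analysis ignores the unit that sets the arm. The direct-effect test is too liberal at any outcome ICC above 0, to roughly twice the nominal level at ICC 0.02 and four times at ICC 0.05 if clinics contribute about 30 women, and less if they contribute 10. The mediated-effect test may be badly inflated, mildly inflated or at its nominal level. Which of these applies depends on the mediator's level and ICC, the reading of the stepwise screen and the true direct effect, and the SAP does not settle it.

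A reader might also infer that the trial's main conclusions are in doubt on this account. They are not: this is an additional analysis, and the Hypothesis 1 and 2 models are specified separately. The consequence falls on statements about mechanism and on the dissemination plan, so the point is one to consider.

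**What to change.** State in Additional analyses that every mediation model accounts for clinic, either by a clinic random effect or by cluster-robust or clinic-bootstrap intervals, in each case with a small-sample correction based on the number of clinics. For any mediator with one value per clinic, fit the arm-to-mediator path on one record per clinic, because a clinic random effect cannot be identified there.

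The section is written in the future tense, so on its face the change can still be made. It needs SAP wording and modest programming, and no new data.

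The price is wider intervals and low power if clinics are few. With 30 women per clinic and outcome ICC 0.02, a test that requires both paths to be significant has the following power:

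- Clinic-level mediator (arm effect 1 SD, mediator effect 0.3 SD): 0.20 with 5 clinics per arm and 0.57 with 10.
- Patient-level mediator (both effects 0.3 SD, mediator ICC 0.05): 0.31 and 0.60.

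A non-significant mediated effect should therefore not be read as evidence that a component does not matter.
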